7.3.4 Safety analyses

Safety will be assessed as defined by the endpoints listed in [Section 2.1.2](#) and 2.2.2 based on the treated set (TS). Safety analyses will be descriptive in nature and will be based on BI standards. All adverse events with an onset between start of treatment will be assigned to the on-treatment period for evaluation. For residual effect period (REP) information is listed in [Section 1.2.2](#).

For all analyses the treatment actually administered (= treatment at onset) to the patient will be used (any deviations from the randomised treatment will be discussed in the minutes of the Report Planning Meeting).

Treatments will be compared in a descriptive way. The placebo group in the safety evaluation will consist of all patients treated with placebo, regardless of the dose group in which they were treated. The test treatment groups will be compared to the placebo group in a descriptive way. Tabulations of frequencies/proportions will be used for the evaluation of categorical (qualitative) data, and tabulations of descriptive statistics will be used to analyse continuous (quantitative) data.

Measurements (such as ECGs, vital signs, or laboratory parameters) or AEs will be assigned to treatments (see [Section 4.1](#)) based on the actual treatment at the planned time of the measurement or on the recorded time of AE onset (concept of treatment-emergent AEs). Therefore, measurements planned or AEs recorded prior to first intake of trial medication will be assigned to the screening period, those between the first trial medication intake and the trial termination date will be assigned to the treatment period. These assignments including

Proprietary confidential information © 2020 Boehringer Ingelheim International GmbH or one or more of its affiliated companies

the corresponding time intervals will be defined in detail in the TSAP. Note that AEs occurring after the last per protocol contact but entered before database lock will be reported to Pharmacovigilance only and will not be captured in the trial database.

Additionally, further treatment intervals (called analysing treatments) may be defined in the TSAP in order to provide summary statistics for other than above periods, such as combined treatments, on-treatment totals, or periods without treatment effects (such as screening and post-study intervals).

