With CTP version 5.0, an interim dose group (dose group 5) of 60 mg tid is inserted between dose group 3 and 4. Dose group BI 70mg tid was not performed.

Section 1.2.2 of the CTP: ...the individual patient's end of trial is 14 days following last dosing with BI 894416 or placebo at the earliest.

All AEs reported between administration of BI 894416 and the individual patient's end of trial will be counted as on-treatment AEs.

The following separate study phases will be defined for the analyses of AEs:

- **Screening** (ranging from 0:00h (midnight) on day of informed consent until first administration time of study drug (BI 894416 or Placebo))
- **On treatment**
 - **BI/Placebo treatment** (separately for each treatment, ranging from the time of first administration of BI 894416/Placebo until 0:00h (midnight) on the day after trial completion date)

The following AE displays will be provided in the report:

Section 15.3 (separately for SRD and MRD part) and Appendix 16.1.13.1.8 (for ClinicalTrials.gov and EudraCT only but combined for SRD and MRD part) of the CTR displays:

In these displays, the on-treatment phase will be analysed (labelled with the name of the study treatment (short label)). Screening will not be included in this analysis.

The following totals will be provided in section 15.3 in addition:

- a total over all on-treatment phases ("Total")
- a total over all on-treatment phases involving BI 894416 ("BI Total")

The following totals will be provided in section 16.1.13.1.8 in addition:

- a total over all on-treatment phases ("Total")
- a total over all on-treatment phases ("Total - SRD part")
- a total over all on-treatment phases ("Total - MRD part")
- a total over all on-treatment phases involving BI 894416 ("BI Total")
- a total over all on-treatment phases involving BI 894416 ("BI Total – SRD part")
- a total over all on-treatment phases involving BI 894416 ("BI Total – MRD part")

In Section 15.4 and Appendix 16.2 (Listings) of the CTR displays the screening period will be included and no totals will be provided.

Tables of vital signs and laboratory values will present results by the above mentioned on-treatment phase.

For detailed information on the handling of the treatments refer to Technical TSAP ADS (analysis data set) plan and Analysis Data Reviewers guide.

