6.6 HANDLING OF MISSING DATA AND OUTLIERS

Handling of missing data and outliers will be performed as described in the CTP, Section 7.5.

The only exceptions where imputation might be necessary for safety evaluation are AE dates. Missing or incomplete AE dates are imputed according to BI standards (see BI-KMED-BDS-HTG-0035 (4)).

Missing data and outliers of PK/█ data are handled according to BI standards (see 001-MCS-36-472_RD-01) (5).

Missing baseline laboratory values will be imputed by the respective values from screening.

Unscheduled measurements of laboratory data or vital signs will be assumed to be repeat measurements of the most recent scheduled measurement (e.g. for follow-up or confirmation of a particular value). Therefore, unscheduled measurements will be assigned to the planned time point of the previous scheduled measurement. Adherence to time windows will be checked via the consistency check listings at the RPM/DBLM.

If single cardiac cycles of an ECG (out of the generally four) are missing, the arithmetic mean for this single ECG will be computed with the reduced (1, 2 or 3) number of cardiac cycles. If all cardiac cycles of an ECG are missing, no imputation will be done.

If replicate ECG recordings are missing, the arithmetic means per time point will be computed with the reduced number (1 or 2) of recordings.

For the classification of the on-treatment QTc/QT intervals into “no new onset” / “new onset” categories, a missing value is obtained only in case that

- (i) all on-treatment values are missing and
- (ii) the baseline value is less than or equal to 500 msec, or missing.

If condition (i) is fulfilled but the baseline value is greater than 500 msec, this case will be categorized as ‘no new onset’. If baseline is missing and the maximum on-treatment QTc interval is greater than 450 msec (or 500 msec for QT interval, respectively), this is classified as a ‘new onset’ in the respective category. If baseline is missing and the maximum QTc interval is less than or equal to 450 msec (or 500 msec for QT interval, respectively), this will be categorized as ‘no new onset’. If baseline is missing, a QTc/QT interval > 500 msec at any time on treatment will be a notable finding.

For placebo patients the missing plasma concentration values will be replaced by 0 for the exposure response analysis. For patients on active drug, missing plasma concentration values with ‘BLQ’ in the comment field will not be replaced.

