6.7 BASELINE, TIME WINDOWS AND CALCULATED VISITS

The baseline value is defined as the last measurement before first administration of BI 894416 (SRD part: value at V3, ptm -3:00, MRD part: value at V3, ptms -17:00, -1:00, -0.05).

Section 6.1 of the CTP: *Exact times of measurements outside the permitted time windows will be documented. The acceptable time windows for screening and the end of trial examination are provided in the CTP Flow Charts.*

If Screening Visit is performed on Day -3 (within 76 hours) prior to administration of trial drug, the ambulatory Visit 2 can be omitted.

Study measurements and assessments scheduled to occur ‘before’ trial medication administration on Day 1 are to be performed and completed within a 3 h-period prior to the trial drug administration (including blank values for PK and biomarkers).

In the SRD part, the acceptable deviation from the scheduled time for vital signs, ECG, and laboratory tests will be ± 15 min for the first 4 h after trial drug administration, ± 30 min thereafter on Day 1 and ± 90 min on Day 2.

The acceptable deviation from the scheduled time for neurological tests in the SRD part is ± 45 min on Day 1 and ± 90 min on Day 2.

Starting from 48 h post administration a time window of ± 120 min will be allowed for all study activities (incl. PK and biomarker sampling) in the SRD part.

In the MRD part, the acceptable deviation from the scheduled time for vital signs, ECG, and laboratory tests will be ± 15 min for the first 4 h after trial drug administration on Day 1

and Day 9, ± 30 min thereafter on Day 1 and Day 9, ± 90 min on Day 2 and on Day 10 and ± 120 min from Day 11 onwards.

The acceptable deviation from the scheduled time for neurological tests in MRD part is ± 4 min on Day 1, and ± 90 min on Day 2.

From Day 3 until Day 8 and from 48 h post last administration on Day 9 a time window of ± 120 min will be allowed for all study activities (incl. PK and biomarker sampling) in the MRD part, except PK samples taken pre dose on Days 5, 7 and 8. Pre dose PK samples are taken within a time window of 15 min prior to drug administration.

Adherence to time windows will be checked via the consistency check listings at the RPM/DBLM.

If Visit 2 is omitted because Visit 1 was performed within 76 hours prior to the trial drug administration, the Visit 1 ECG data were transferred as Visit 2 data.

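### An unscheduled laboratory or vital-sign value drawn soon after the first dose takes a pre-dose planned time, and the plan does not settle whether it counts as on treatment

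*SAP*

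**What the plan says.** **Handling of unscheduled values.** SAP 6.6 starts from an assumption: "Unscheduled measurements of laboratory data or vital signs will be assumed to be repeat measurements of the most recent scheduled measurement". It concludes: "Therefore, unscheduled measurements will be assigned to the planned time point of the previous scheduled measurement". No exception is made for a value whose previous scheduled measurement lies on the other side of the first dose.

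**Allocation to periods.** Protocol 7.3.4 allocates measurements and adverse events (AEs) to treatment "based on the actual treatment at the planned time of the measurement or on the recorded time of AE onset". It adds that "measurements planned or AEs recorded prior to first intake of trial medication will be assigned to the screening period". The same paragraph leaves the details of these assignments and intervals to the SAP.

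**On-treatment phase.** SAP 6.1 defines this phase by the clock, "ranging from the time of first administration of BI 894416/Placebo until 0:00h (midnight) on the day after trial completion date". The phases are introduced for the AE analyses, but the section then says: "Tables of vital signs and laboratory values will present results by the above mentioned on-treatment phase".

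**Baseline.** SAP 6.7 states: "The baseline value is defined as the last measurement before first administration of BI 894416". A parenthesis then ties this to planned times at Visit 3: -3:00 in the SRD part and, for the other part, "MRD part: value at V3, ptms -17:00, -1:00, -0.05". I read the last of these as -0:05.

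**The concern.** The rule in SAP 6.6 is reasonable when an unscheduled value really does repeat the last scheduled one. It fits poorly when the extra sample is prompted by something that happened after dosing. The protocol foresees such samples: section 6.1 allows extra visits for AE monitoring, and section 5.2.6.1.4 asks for unscheduled liver tests if symptoms suggest hepatic injury. A sample of that kind, taken soon after the first dose, is not a repeat of the pre-dose sample, yet it would carry the pre-dose planned time.

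Two things are then open. The value may or may not appear in the on-treatment laboratory and vital-sign tables, depending on which document the programmer follows. And because its planned time is one that SAP 6.7 names for baseline, a program that selects baseline by planned time could pick it up. Safety and tolerability is the primary objective, and each dose group has 8 patients on active drug, so one patient is 1/8 = 12.5% of a group.

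**Working it through.** The plan gives no figure to reproduce. The check applies the SAP 6.6 rule to the scheduled times in the protocol's flow charts, then asks which period each document would assign.

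**Rule applied.** Assigned time = latest planned time at or before the actual draw.

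**Scheduled laboratory times, from the time schedules (h:min from first dose):**
- SRD: -3:00, 4:00, 24:00, 48:00, 168:00.
- MRD: -0:05, 23:55, 47:55, 95:55, 167:55, 240:00, 288:00.

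**Draws after the first dose that receive a pre-dose time:**

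| Data | Window after first dose | Assigned time |
|---|---|---|
| SRD laboratory | 0 to 4:00 h | -3:00 |
| MRD laboratory | 0 to 23:55 h | -0:05 |
| SRD vital signs | 0 to 0:30 h (columns read from a broken table) | -3:00 |
| MRD vital signs, Day 1 | not readable in the text available | n/a |

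**Size of the laboratory windows.** Protocol 1.2.2 gives a terminal half-life of 2.96 to 5.31 h from the earlier healthy-volunteer trial.
- SRD: 4/5.31 = 0.75 to 4/2.96 = 1.35 half-lives.
- MRD: 23:55 h = 23.92 h, so 23.92/5.31 = 4.5 to 23.92/2.96 = 8.1 half-lives after the Day 1 dose.
- The MRD window is 23.92/192 = 12.5% of the time from first to last dose.

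**Draws outside these windows stay on treatment.** An SRD laboratory draw at 6 h goes to 4:00; MRD draws at 30 h and 100 h go to 23:55 and 95:55. They can be dated too early (an MRD Day 7 sample is tabulated at 95:55, on Day 5) but they do not change period.

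**The same value under each text.** Take an MRD sample drawn 6 h after the first dose and assigned to -0:05.
- Protocol 7.3.4, by planned time: screening.
- SAP 6.1, by clock time: on treatment.
- SAP 6.7, main sentence: not baseline, since it was taken after dosing.
- SAP 6.7, parenthesis: its planned time is one of those listed for baseline.

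**Illustration of the baseline risk, with assumed ALT values.** Pre-dose 25, unscheduled 2 h value 60, later scheduled value 65. The correct change is 65 - 25 = +40. If a program chose baseline by planned time and took the 60, the reported change would be 65 - 60 = +5. The main sentence of SAP 6.7 does not permit this, so it shows only what a program keyed to the parenthesis could do.

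**The case against.** The strongest reply is that the SAP already answers the question. Protocol 7.3.4 hands the detail to the SAP, SAP 6.1 starts the on-treatment phase at the time of first administration, and it applies that phase to the laboratory and vital-sign tables. On that reading a value drawn 2 h after dosing is on treatment and cannot be baseline. This has weight, and it rules out saying that such values definitely leave the on-treatment tables. It does not close the gap. SAP 6.1 introduces its phases for AEs, and neither document says whether the assigned or the actual time fixes the phase of a reassigned value. The time-window check at the report planning and database lock meetings comes with no reassignment rule.

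The safeguards cited on the other side also stand. Individual values are listed and out-of-range values flagged. Findings judged clinically relevant become AEs, allocated by onset time, and hepatic injury alerts are tabulated separately as events of special interest. The safety monitoring committee reviews individual data before each escalation. SAP 7.8.2 summarises the worst value per visit, and pre-dose and early post-dose samples both belong to Visit 3, so a literal by-visit summary might still hold the value.

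A reader might infer more than the documents support:
- *Every unscheduled value is lost from the on-treatment tables.* Only draws in the windows above can receive a pre-dose time.
- *The error always makes the drug look safer.* If a relabelled value did reach baseline, one below the true baseline would make later increases look larger.
- *The windows cover the concentration peak.* The documents give no time of peak.
- *Reference-range counts lose these values.* SAP 7.8.2 describes flags in listings; the tabulation rules sit in a sponsor standard that is not available here.

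**Conclusion.** The point holds in a limited form. Nothing in either document stops the SAP 6.6 reassignment from crossing the first dose. For laboratory draws up to 4:00 h (SRD) or 23:55 h (MRD) after first dosing, the protocol's planned-time rule and the SAP's clock-time phase give different answers, so two programmers could produce different tables from the same data. The gap matters most for MRD laboratory data, where it takes in nearly all of the first 24 hours.

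The consequence is confined to descriptive laboratory and vital-sign tables. Listings, AE tables and the primary endpoint, the percentage of patients with drug-related AEs, are unaffected, and the trial tests no hypotheses. I rate it minor to moderate.

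This rests on three assumptions: that the laboratory times are read correctly from time schedules whose columns are partly displaced; that at least some unscheduled samples fall in these windows, a number the documents do not give; and that the separate analysis-data plan, not available here, does not already settle the matter.

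**What to change.** Add to SAP 6.6:
- An unscheduled value is never reassigned across the first dose.
- Its phase (pre-dose or on treatment) and its eligibility as baseline are decided by actual date and time relative to first administration.
- Unscheduled post-dose values count in the on-treatment laboratory and vital-sign summaries.

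A cross-reference in SAP 6.1 and 6.7 would make clear that the listed planned times do not override this. The cost is one short paragraph and a small change in the analysis-data programming. It needs the actual times of unscheduled measurements, which SAP 6.6 already presupposes by ordering them against the schedule. No new data collection and no change to trial conduct is involved.

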6.7 BASELINE, TIME WINDOWS AND CALCULATED VISITS

The baseline value is defined as the last measurement before first administration of BI 894416 (SRD part: value at V3, ptm -3:00, MRD part: value at V3, ptms -17:00, -1:00, -0.05).

Section 6.1 of the CTP: *Exact times of measurements outside the permitted time windows will be documented. The acceptable time windows for screening and the end of trial examination are provided in the CTP Flow Charts.*

If Screening Visit is performed on Day -3 (within 76 hours) prior to administration of trial drug, the ambulatory Visit 2 can be omitted.

Study measurements and assessments scheduled to occur ‘before’ trial medication administration on Day 1 are to be performed and completed within a 3 h-period prior to the trial drug administration (including blank values for PK and biomarkers).

In the SRD part, the acceptable deviation from the scheduled time for vital signs, ECG, and laboratory tests will be ± 15 min for the first 4 h after trial drug administration, ± 30 min thereafter on Day 1 and ± 90 min on Day 2.

The acceptable deviation from the scheduled time for neurological tests in the SRD part is ± 45 min on Day 1 and ± 90 min on Day 2.

Starting from 48 h post administration a time window of ± 120 min will be allowed for all study activities (incl. PK and biomarker sampling) in the SRD part.

In the MRD part, the acceptable deviation from the scheduled time for vital signs, ECG, and laboratory tests will be ± 15 min for the first 4 h after trial drug administration on Day 1

and Day 9, ± 30 min thereafter on Day 1 and Day 9, ± 90 min on Day 2 and on Day 10 and ± 120 min from Day 11 onwards.

The acceptable deviation from the scheduled time for neurological tests in MRD part is ± 4 min on Day 1, and ± 90 min on Day 2.

From Day 3 until Day 8 and from 48 h post last administration on Day 9 a time window of ± 120 min will be allowed for all study activities (incl. PK and biomarker sampling) in the MRD part, except PK samples taken pre dose on Days 5, 7 and 8. Pre dose PK samples are taken within a time window of 15 min prior to drug administration.

Adherence to time windows will be checked via the consistency check listings at the RPM/DBLM.

If Visit 2 is omitted because Visit 1 was performed within 76 hours prior to the trial drug administration, the Visit 1 ECG data were transferred as Visit 2 data.

There will be a centralised evaluation of the 12-lead ECG recordings at the time points and for the ECG recordings specified in the [Table 6.7: 1](#) and the [Table 6.7:2](#) below:

Table 6.7: 1 Time schedule of 12-lead ECG recordings – SRD part

Visit	Day	Planned time [hh:mm] (relative to drug administration)	Study phase	Central evaluation
1	-28 to -3		Screening	NA
2	-3 to -1	-72:00	Pre-treatment	All three ECGs of the triplicate
		-71:45	Pre-treatment	All three ECGs of the triplicate
		-71:30 (separated by at least 15minutes)	Pre-treatment	All three ECGs of the triplicate
3	1	-3:00	Baseline	All three ECGs of the triplicate
		0:30	On treatment	first single ECG of the triplicate
		1:00	On treatment	first single ECG of the triplicate
		1:30	On treatment	first single ECG of the triplicate
		2:00	On treatment	first single ECG of the triplicate
		2:30	On treatment	first single ECG of the triplicate
		3:00	On treatment	first single ECG of the triplicate
		4:00	On treatment	first single ECG of the triplicate
		6:00	On treatment	first single ECG of the triplicate
		8:00	On treatment	first single ECG of the triplicate
		12:00	On treatment	first single ECG of the triplicate
	2	24:00	On treatment	first single ECG of the triplicate
		34:00	On treatment	NA
4	3	48:00	On treatment	NA
5	4	72:00	On treatment	NA
8	15-17		End of trial examination	NA

At Visit 1 single ECGs will be recorded.

At Visit 2 and Visit 3 (up to planned time 24:00h) triplicate ECGs will be recorded. For the four pre-dose triplicate ECGs all three single ECGs will be evaluated. For the other triplicate ECGs only the first single ECG will be evaluated.

At Visit 3 (planned time 34:00h) and Visits 4-8, single ECGs will be recorded.

Table 6.7: 2 Time schedule of 12-lead ECG recordings – MRD part

Visit	Day	Planned time [hh:mm] (relative to drug administration)	Study phase	Central evaluation
1	-28 to -3		Screening	NA
3	-1	-17:00	Pre-treatment	All three ECGs of the triplicate
		-16:45	Pre-treatment	All three ECGs of the triplicate
		-16:30	Pre-treatment	All three ECGs of the triplicate
		(separated by at least 15minutes)		
		-1:00	Baseline	All three ECGs of the triplicate
3	1	0:30	On treatment	first single ECG of the triplicate
		1:00	On treatment	first single ECG of the triplicate
		1:30	On treatment	first single ECG of the triplicate
		2:00	On treatment	first single ECG of the triplicate
		2:30	On treatment	first single ECG of the triplicate
		3:00	On treatment	first single ECG of the triplicate
		4:00	On treatment	first single ECG of the triplicate
		6:00	On treatment	first single ECG of the triplicate
		8:00	On treatment	first single ECG of the triplicate
		12:00	On treatment	first single ECG of the triplicate
	2	24:00	On treatment	first single ECG of the triplicate
	2	34:00	On treatment	NA
	3	47:00, 56:00, 58:00	On-treatment	NA
	4	70:30, 80:00	On-treatment	NA
	5	104:00	On-treatment	NA
	6	128:00	On treatment	NA
	7	152:00	On treatment	NA
	8	176:00	On treatment	NA
	9	191:55	On treatment	first single ECG of the triplicate
		192:30	On treatment	first single ECG of the triplicate
		193:00	On treatment	first single ECG of the triplicate
		193:30	On treatment	first single ECG of the triplicate
		194:00	On treatment	first single ECG of the triplicate
		194:30	On treatment	first single ECG of the triplicate
		195:00	On treatment	first single ECG of the triplicate
		196:00	On treatment	first single ECG of the triplicate
		198:00	On treatment	first single ECG of the triplicate

Table 6.7: 2 Time schedule of 12-lead ECG recordings – MRD part - continued

Visit	Day	Planned time [hh:mm] (relative to drug administration)	Study phase	Central evaluation
		200:00	On treatment	first single ECG of the triplicate
		204:00	On treatment	first single ECG of the triplicate
	10	216:00	On treatment	first single ECG of the triplicate
4	11	240:00	On treatment	NA
5	12	264:00	On treatment	NA
6	13	288:00	On treatment	NA
7	16	-	On treatment	NA
8	23-30	-	On treatment	NA

For the four pre-dose triplicate ECGs all three single ECGs will be evaluated. For the other triplicate ECGs only the first single ECG will be evaluated.

Section 5.2.5.1 of the CTP: *Central ECG lab evaluation will be performed (during the study and/or after the study) for the first of three replicate ECGs per time point. For baseline, all three ECGs of the triplicate ECG on Day 1 pre-dose will be evaluated. For the three triplicate ECGs on Day -3 to -1 all ECGs will be evaluated. This will include the determination of cardiac QRSaxis as assessed by the ECG machine's algorithm as well as the intervals RR, PR, QRS and QT measured semi-automatically. Heart rate (HR) and the QT interval corrected for HR (QTc e.g. QTcF and QTcB) will be determined by the sponsor.*

For the exposure response analyses, pairs of ECG variables and corresponding plasma concentrations will be built using the same planned time points, e.g. HR change from baseline and the plasma concentration measured at planned time 1:00 will build one pair.

Whether a time deviation between PK blood sampling time and corresponding ECG recording is too big and the pair has to be excluded from the analysis will be decided no later than at the RPM. This critical time deviation depends on the PK properties. When plasma concentrations are expected to change only little around a given time point, the acceptable time deviation between ECG recording and PK blood sampling may be bigger.

